Department of Endocrinology and Diabetes, St Helens Hospital, Mersey and West Lancashire Teaching Hospitals NHS Trust.	Funded clinical research fellow post and PhD fees at University of Liverpool. Postage costs for patient information sheets to patients

Roles and Responsibilities of Study Sponsor and Funder

The sponsor of this study is University of Liverpool where the researcher is currently registered on her full-time

3-yr PhD. The University of Liverpool is a member of the prestigious Russell Group of UK research intensive institutions and is internationally recognised with 91% of its research being ranked as world-leading and internationally excellent in the latest Research Excellence Framework. As the study sponsor, the University of Liverpool is responsible for the initiation and management of the research and takes primary responsibility for ensuring that the design of the study meets appropriate standards.

The funder is the Diabetes Centre, St Helens Hospital, Mersey and West Lancashire Teaching Hospitals NHS Trust who will provide the working environment and resources for the clinical research fellow post to which the researcher is employed.

Service user involvement

The DIABETES-PRO study design and justification have been discussed with a service user living with diabetes. Having completed previous education programmes they were shocked by the low number that attend DSME programmes and that a record of 'attended' required minimal engagement with a programme, or that a patient is classes as 'completed' following engagement with >60% of a programme. The service user was reassured that all patients would be offered a full education programme at the end of the study and thought the offer of a home visit or telephone appointment to reduce the burden on patients to attend an additional appointment at the end of the study (follow up visit) was important.

Templates from the Health Research Authority (HRA) have been adopted for use in this study to ensure that participant information sheets and consent forms are easy to read and contain the required information to support participants in making an informed choice.

Peer review

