6.2 Study processes

Screening and recruitment

Potentially eligible participants meeting the inclusion criteria and not excluded by exclusion criteria (outlined in section 8.1) who are either due to attend the diabetes centre for new patient clinic, have been referred for DSME intervention or are on the monthly shared care report for newly diagnosed type 2 diabetes requiring an offer of DSME will be screened for entry into the study and added to a screening log sheet (appendix 1). Potentially eligible participants due to attend new patient clinic will be invited into the study by NP clinic letter (appendix 1) with attached participant information sheet (PIS) (appendix 1). Letters will be posted ahead of their clinical appointment. For potential eligible participants identified through DSME referrals or the monthly shared care record report will be sent a telephone screening letter (Appendix 1) and PIS prior to meeting with the researcher. Study recruitment technique is outlined in further detail in section 8.2.2.

At the screening meeting potentially eligible participants will be asked to confirm they have read the PIS and invited to ask questions about the research. Where patients decline to take part in the research, they will be reassured this will not have any impact on their current or future treatment. Participants who give written informed consent will be enrolled onto the study. The researcher will utilise an informed consent checklist (Appendix 1) to ensure consistency and that all elements for informed consent have been completed. Participants will be consented for informing their GP, this is made clear in the PIS.

Visit 1

At enrolment baseline characteristics will be recorded from the electronic medical record, or where not available directly from the patient: NHS number, age, sex, ethnicity, diabetes duration, postcode, latest HbA_{1c}, prescribed glucose lowering agents, and a Charlson Comorbidity Index will be calculated. Postcode will be used to calculate indices of multiple deprivation (IMD) score.

Participants (n=120) will be randomised by permuted block strategy of 2:1 across four groups using an online randomisation software application designed for clinical trials (51,52). Due to the design of this study randomisation will not be blind to the researcher or participants. Group design will be as follows:

- Group 1: DSME 6 hours, 100% completed (completed).
- Group 2: DSME 3 hours 36 minutes, 60% completion (partial completion)

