- Group 3: DSME 36 minutes, 10% of content (attended)
- Group 4: Delayed education (education not offered, not attended, or declined)

DSME programme overview is provided in appendix 1 giving a broad overview of DSME content by programme completion status. Local demographic data suggests that of the local population 46.4% are living in the most deprived neighbourhoods within the UK (9). Of the local population 19.3% have a reading age of 9-11 or below (53,54), are classed as being functionally illiterate and are therefore likely to struggle reading a paper questionnaire. Verbal support for completing the PROMs will be offered by the researcher to ensure participants from lower socioeconomic backgrounds are not excluded from participating in the DIABETES PRO study as they are evidenced to make up a larger proportion of people with diabetes (55-57). Support will be limited to reading the questions verbatim.

Participants will be asked to complete three psychometric tests measuring self-care activities, diabetes distress and quality of life using the following validated tools: Diabetes Self-Management Questionnaire-Revised (DSMQ-R)(48), Problem Areas in Diabetes (PAID) scale (49) and the Patient Reported Outcome Measures Information System (PROMIS) Global Health scale v1.2 (50) (appendix 1).

Participants in groups 1, 2 and 3 will be asked to book a DSME session with the researcher, typically this should be no longer than 3 weeks from study enrolment. Research group DSME programmes (intervention) will be run by the researcher separate to routine patient DSME to minimise disruption of participants leaving part way through on patients.

Participants randomised to group 4, delayed education will not be required to attend DSME as part of the DIABETES PRO study. Collected data will be collected and managed using Research Electronic Data Capture (REDCap) electronic data capture tools. A REDCap data collection tool has been included in Appendix 1 for reference. REDCap is a secure, web-based software platform designed to support data capture for research studies, providing an intuitive interface for validated data capture; audit trails for tracking data manipulation and export procedures; automated export procedures for seamless data downloads to common statistical packages; and procedures for data integration and interoperability with external sources (58,59) (see section 3.6 for further details).

Visit 2

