Intervention • How is the intervention different from normal care? • What does it look like? • Is it clear when it starts and finishes?	Clinical intervention of participants will not be altered. Participants will receive the same DSME programme as routine clinical patients. Normal delivery of DSME programmes is by a diabetes specialist nurse or dietitian. Research DSME programmes will be, where possible, delivered by the researcher for consistency. Participants will be reminded at the beginning of the DSME programme that this is a research study and that some participants will leave after 36 minutes, 3 hours and 36 minutes, with others remaining for the full 6 hours programme. Reminders will be given at the time points in which participants from groups 2 and 3 should leave.
Contextual information • Policy initiatives related to the intervention?	DSME is NICE recommended for all patients newly diagnosed with type 2 diabetes with annual refresher thereafter (15). The National Diabetes Audit suggests 71% of people with type 2 diabetes are offered DSME, with an average attendance rate of 7%. Local records suggest that of those that start DSME (9%) only 12.6% complete the programme (20).

Visit 3

Between 3-4 months post intervention participants will be asked to repeat baseline psychometric tests. For participants in group 4 this will be 4 months from enrolment. This will be the end of the study.

At the end of the study participants in groups 2, 3 and 4 will be offered a full DSME programme.

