6.3 Data Collection

A REDCap data capture template has been created for collection and analysis and included in Appendix 1. REDCap which provides a secure platform for clinical research studies (58,59) will be utilised for data capture. Screening and baseline demographics will be obtained from the patient electronic record system, if any demographic information is unavailable this will be collected direct from the participant. Paper questionnaires will be completed by hand by study participants supported by the researcher and subsequently entered on the

data capture sheet by the researcher (example data capture template in appendix 1). To ensure consistency of the data being collected DIABETES-PRO pathway checklists will be used for visits 1, 2 and 3 (appendix 1).

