9.1 Definitions

Adverse Event (AE): any untoward medical occurrence in a patient or clinical study subject, including unfavourable and unintended signs, including abnormal laboratory results, symptoms or a disease associated with treatment.

Serious Adverse Event (SAE): any untoward and unexpected medical occurrence or effect that:

- **Results in death**
- **Is life-threatening** – refers to an event in which the subject was at risk of death at the time of the event; it does not refer to an event which hypothetically might have caused death if it were more severe
- **Requires hospitalisation, or prolongation of existing inpatients' hospitalisation**
- **Results in persistent or significant disability or incapacity**

- **Is a congenital anomaly or birth defect**

A risk assessment has been carried out for this study. Risks are scored according to severity and likelihood giving an overall risk score (please see figure 5). Identified risks are detailed in table 4.

Peer review feedback highlighted the risk of the researcher knowingly or unknowingly biasing results by supporting participants to complete the PROM tools. This has been risk assessed in table 5. To ensure transparency, support from the researcher will be limited to reading the questions verbatim for each of the PROM tools. This will be done for every participant to standardise the approach.

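### The unblinded researcher who teaches the sessions also supports and enters the self-report outcomes, so favourable answering may rise with allocated dose and could mimic a dose response

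*Combined protocol and SAP*

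**What the plan says.** Section 6.2 (Visit 1) states that "Due to the design of this study randomisation will not be blind to the researcher or participants". It then says that "Research group DSME programmes (intervention) will be run by the researcher separate to routine patient DSME"; Table 2 in the same section softens this to "Research DSME programmes will be, where possible, delivered by the researcher for consistency". Contact with the teacher during the study is therefore 360 minutes in Group 1, 216 in Group 2, 36 in Group 3 and none in Group 4.

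The primary outcome (section 5.2) is change in the DSMQ-R. The secondary outcomes are the PAID and PROMIS Global Health scales. All three are self-reported.

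On how they are completed:

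- Section 6.2: "Verbal support for completing the PROMs will be offered by the researcher". The stated reason is local literacy, and support is confined to verbatim reading.
- Section 6.3: "Paper questionnaires will be completed by hand by study participants supported by the researcher". The researcher then enters the answers.
- Section 9.1, on the bias raised at peer review, repeats the verbatim limit and adds: "This will be done for every participant to standardise the approach".
- Table 5 names one risk, that the researcher influences how questions are understood. It lists one control, verbatim reading, gives a residual score of 1 x 2, and asks for no further controls.

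The protocol text describes no private completion, no independent administrator and no masked data entry.

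**The concern.** Verbatim reading keeps the researcher from rewording items. It does nothing about a participant who reports better self-care because the person who taught them is in the room and will handle the sheet. A uniform procedure does not make this cancel between groups, because the relationship with the researcher differs by design: Group 1 has spent six hours with them as a teacher and Group 4 none.

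If the tendency to answer favourably grows with that contact, the bias has the same ordering as the exposure under study, and an analysis of change scores cannot separate the two. The damage is not limited to a false-positive test. Section 8.2.1 says the sample is meant to estimate effect sizes for later research, so a distorted gradient would be carried into the design of the full trial.

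The text also leaves unclear who is read to. Section 6.2 describes an offer. Section 9.1 can be taken to mean that everyone is read to, or that the verbatim limit applies to everyone who is helped.

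**Working it through.** **Inputs from the protocol.** 30 per group, 120 in total (8.2.1): 4 x 30 = 120, which reproduces. Contact times (6.2): 0.60 x 360 = 216 minutes and 0.10 x 360 = 36 minutes, which also reproduce. Analysis: ANOVA of the pre-post difference across four groups, alpha 5% (6.4). No power, SD or effect size is stated, so there is no power figure to check.

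**Assumptions, not in the documents.** No true effect. SD of change set to 1. A reporting bias at follow-up proportional to contact time: b x (1.0, 0.6, 0.1, 0) for Groups 1 to 4, where b is the bias in Group 1 in SD of change. All 30 per group are analysed, and the researcher teaches every session.

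**Planned four-group ANOVA.** The mean of the weights is (1.0 + 0.6 + 0.1 + 0)/4 = 0.425. The squared deviations are 0.330625, 0.030625, 0.105625 and 0.180625, which sum to 0.6475. Noncentrality is 30 x b² x 0.6475 = 19.425 b², on 3 and 116 df, with critical F 2.683.

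| b (SD of change) | Noncentrality | Rejection rate, no true effect |
|---|---|---|
| 0 | 0 | 5.0% |
| 0.1 | 0.194 | 6.1% |
| 0.2 | 0.777 | 9.8% |
| 0.3 | 1.748 | 16.8% |

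At 24 per group, the lower end of the range cited in 8.2.1, the rates for b = 0.1, 0.2 and 0.3 are 5.9%, 8.8% and 14.1%.

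**The comparisons the protocol asks about.** Sections 3 and 5 ask about 10% v no attendance (Group 3 v 4) and 60% v 100% (Group 2 v 1). For a two-sided t test on 58 df, the noncentrality is the bias difference divided by √(2/30) = 0.258.

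| Comparison | Bias difference | b = 0.2 | b = 0.3 |
|---|---|---|---|
| Group 3 v 4 | 0.1b = 0.02 / 0.03 SD | 5.1% | 5.1% |
| Group 1 v 2 | 0.4b = 0.08 / 0.12 SD | 6.1% | 7.4% |

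Group 1 v Group 4 would give 11.9% and 20.8%, but the plan does not name that comparison, so it is not used as the measure of size.

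**The case against.** **The gradient is inferred.** No passage shows that favourable answering rises with minutes of contact. Sessions are group-based, Groups 2 and 3 are asked to leave partway, and Groups 2 to 4 are still due a full programme afterwards, so attitudes to the researcher need not be ordered by dose. Delivery by the researcher is only where possible, and the Visit 3 text does not say who administers the questionnaires; sections 6.3 and 9.1 imply the researcher. This stands, and the point is therefore worded as a bias that may rise with dose.

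**Sections 6.2 and 9.1 may not conflict.** A reader might infer a flat contradiction, with everyone read to in one section and only those who want it in the other. Section 9.1 can equally mean that the verbatim limit applies to everyone. The documents support an ambiguity to be resolved, no more.

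**Telephone completion.** A reader might infer that follow-up answers will be given by telephone. The only basis is a service-user comment welcoming "the offer of a home visit or telephone appointment to reduce the burden on patients"; the Visit 3 text specifies no telephone completion.

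**The risk is already assessed, and participants write their own answers.** Both are true. Writing by hand limits the effect, but it does not remove it when the teacher is present and enters the form. Table 5 covers only how items are understood. The visit checklists might specify privacy or mode, but they are in separately supplied appendices and cannot be seen here.

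**It is an unpowered feasibility study.** Section 6.1 says so. The plan nevertheless tests at 5% and intends to estimate effects, and trying out the outcome-collection procedure is part of what a feasibility study is for.

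**Conclusion.** The point holds in a limited form. The same unblinded person teaches (where possible), supports completion of the self-report outcomes and enters them, and the one listed control does not address answering to please. Under an assumed bias proportional to contact that reaches 0.1 to 0.3 SD in Group 1, the planned ANOVA's false-positive rate rises from 5% to between 6.1% and 16.8%. At 0.2 to 0.3 SD the 10% v none comparison is almost untouched (about 5.1%) and the 60% v 100% comparison moves modestly (6.1% to 7.4%). Both the size and the shape of the bias are assumptions.

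A reader might infer that the bias does rise with dose, or that the results will be uninterpretable. The documents support neither. They support an avoidable risk that is cheap to reduce. Bias from participants knowing their own allocation will remain whatever is done.

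**What to change.** 1. In sections 6.3 and 9.1 and in Table 5, state that at Visits 1 and 3, whether or not items are read aloud, the participant marks the paper out of the researcher's sight and seals it in an envelope labelled with study ID only.
2. State that data entry is done without reference to group. Because the researcher also holds the log linking ID to group, this reduces the link and does not break it.
3. Reconcile sections 6.2 and 9.1 so that it is clear who is read to.
4. Record the mode of completion at both visits (self-completed, read aloud, or telephone if it is ever used).
5. State the residual bias from unblinded participants as a limitation, and add answering in front of the teacher as a named risk in Table 5.

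The choice between reading to everyone and reading on request is a trade-off for the sponsor: the first keeps the mode uniform, the second limits exposure to those who need help. Excluding read-aloud responses from an analysis is not recommended as a remedy, since it would drop the low-literacy participants that section 6.2 sets out to include. At the 19.3% quoted there for the local population, that would be about 0.193 x 120 = 23 people.

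Cost: wording changes, envelopes and one extra data field, with no extra staff. Skipped items can no longer be spotted on the day, and private marking cannot apply to any telephone completion.

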9.2 Reporting procedures

All adverse events will be reported. Depending on the nature of the event the reporting procedures below will be followed. Any questions concerning adverse event reporting should be directed to the Chief Investigator in the first instance.

9.2.1 Non-serious Adverse Events (AEs)

Potential Adverse Events (AEs) are outlined in table 5.

All such events, whether expected or not, will be recorded on a Case Report Form (CRF) and in the patient's medical notes.

9.2.2 Serious Adverse Events (SAEs)

No serious adverse events are anticipated for this study. Upon identification of an SAE the researcher would complete a study specific SAE form which would be sent to the Chief Investigator within 24 hours.

Contact details for reporting SAEs

[contact], attention [name]

Please send SAE forms to: [contact]

[contact] (Mon to Fri 09.00 – 17.00)

All SAEs will be reported to the REC where in the opinion of the Chief Investigator, the event was:

- **'related'**, i.e. resulted from the administration of any of the research procedures; and
- **'unexpected'**, i.e. an event that is not listed in the protocol as an expected occurrence

Reports of related and unexpected SAEs will be submitted within 15 days of the Chief Investigator becoming aware of the event, using the [HRA Non-CTIMP safety report to REC form](#). The Chief Investigator will also notify the Sponsor of all SAEs.

For NHS REC approved studies please refer to <https://www.hra.nhs.uk/approvals-amendments/managing-your-approval/safety-reporting/> - (Scroll to Safety reporting for non-CTIMP studies)

Impact Score	Likelihood /probability				
	1 Rare	2 Unlikely	3 Possible	4 Likely	5 Almost certain
5 Catastrophic	5	10	15	20	25
4 Major	4	8	12	16	20
3 Moderate	3	6	9	12	15
2 Minor	2	4	6	8	10
1 Negligible (very low)	1	2	3	4	5

Likelihood – Descriptor and definition
Almost certain - More likely to occur than not, possibly daily (>50%)
Likely - Likely to occur (21-50%)
Possible - Reasonable chance of occurring, perhaps monthly (6-20%)
Unlikely - Unlikely to occur, may occur annually (1-5%)
Rare - Will only occur in exceptional circumstances, perhaps not for years (<1%)
Impact - Descriptor and definition
Catastrophic – Serious trust wide failure possibly resulting in patient deaths / Loss of registration status/ External enquiry/ Reputation of the organisation seriously damaged- National media / Actual disruption to service delivery/ Removal of Board
Major – Significant negative change in Trust performance / Significant deterioration in financial position/ Serious reputation concerns / Potential disruption to service delivery/Conditional changes to registration status/ may be trust wide or restricted to one service
Moderate – Moderate change in Trust performance/ financial standing affected/ reputational damage likely to cause on-going concern/potential change in registration status
Minor – Small or short term performance issue/ no effect of registration status/ no persistent media interest/ transient and or slight reputational concern/little financial impact.
Negligible (very low) – No impact on Trust performance/ No financial impact/ No patient harm/ little or no media interest/ No lasting reputational damage.

Figure 5: Risk assessment template and legend

Table 4: Potential participant adverse study events and controls.

Risk	Initial Risk Score	Key Controls	Sources of Assurance	Residual Risk Score	Additional Controls Required	Additional Assurance Required	Action Plan (with target completion dates)	Target Risk Score
Participants become distressed after completing patient reported outcome measures highlighting diabetes distress	3 x 1	The use of PROMs selected for use within this study are validated tools approved for use in clinical practice however it may be possible that a participant becomes distressed if a score is not anticipated e.g., diabetes distress highlighted. Where participants are highlighted as having high levels of distress then a letter will be sent to their GP with their permission highlighting further support may be needed. Participants will also be given contact details for St Helens Think Well-Being team.	Validated PROMs designed for use measuring diabetes distress, quality of life and self-care abilities which have been used and designed in collaboration with people with diabetes. Psychological support pathway already in place locally.	3 x 1	None needed	None needed	Progress as planned	3 x 1
As a result of delayed or incomplete DSME participants are unable to adequately manage their diabetes	4 x 2	There is a national NICE recommended target to offer all patients DSME within 12 months of diagnosis. This study will potentially delay DSME access by 4 months, less than the nationally recommended 12 months. All participants will be offered a full DSME programme at the end of the study. As a result of participating in this study participants are likely to gain access to DSME sessions quicker than those on the routine waiting list.	DSME offers and attendance are recorded locally and are reported nationally via the National Diabetes Audit. Database will be monitored weekly to ensure no unnecessary delay in offering DSME programmes following completion of the research.	3 x 1	None needed	None needed	Progress as planned	3 x 1
As a result of the DSME programme participants worry about the impact of diabetes on their long-term health	2 x 1	DSME sessions are taught by health care professionals with experience working with people with diabetes and will be able to offer any advice and reassurance as required. As part of the DSME programme all participants will receive a short booklet about managing their diabetes at the start of the programme.	Education sessions will be QISMET accredited and are designed to support behavioural changes with patients. Information about the seriousness of diabetes is delivered sensitively to by trained health care professionals with experience in teaching.	2 x 1	None needed	None required	Progress as planned	2 x 1
Participants are concerned about how their data will be used and if they will be identifiable	3 x 3	Participants will be reassured as part of the screening and recruitment process about how data is handled and that a pseudocode will be used at the point their data is entered onto the study database. Only the researcher will have access to the cross-identifier checklist. Participants will be reminded that they are free to withdraw from the study at any point at which no further data about them will be collected.	Participant information sheet, consent form and data management plan.	2 x 1	None needed	None needed	Progress as planned	2 x 1

Table 5: Potential researcher bias risk assessment and controls.

Risk	Initial risk score	Key controls	Residual risk score	Additional controls required	Additional assurance required	Action plan	Target risk score
Researcher knowingly or unknowingly influences participants understanding of questions in an effort to support completion of item.	2 x 2	Researcher support will be limited to reading tool questions verbatim.	1 x 2	None needed	None needed	Progress as planned	1 x 2

